## **Randomization and sample size**

Randomization of participants is performed by independent third parties (two nurse assistants at the outpatient clinic). All patients scheduled for THA and TKA attending the outpatient clinic are considered eligible and invited to participate in randomization if they meet the inclusion criteria. Eligible patients will draw one of two cards; one indicate an invitation to participate the study and the other is blank, indicating no participation in the study. Patients in the control group will be recruited every other week and patients for the intervention group every week between. This pattern will be repeated until the desired number of patients are recruited. This stratification will ensure that patients in different groups do not exchange information in the postoperative ward. The sample size requirement for comparing two means was checked with power analysis (2-sided test) with  $\alpha = 0.05$ ,  $\beta = 0.9$ , standard deviation 0.08, and differences of means 0.03 in 15D scores, which is within the slight difference of 0.015-0.035 (Alanne, Roine, Räsänen, Vainiola, & Sintonen, 2015). A sufficient sample size is determined to be 152 per group.

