### **Secondary Outcome Measures**

1. Change from baseline Surgery-related anxiety at three months after the surgical procedure. Time frame: Baseline 2-3 weeks prior to, and post-measurement 3 months after the procedure (The State-Trait Anxiety Inventory (STAI))
2. Quality of perioperative care as experienced by surgical patients. Time frame: On average the third postoperative day, depending the time of discharge (Good Perioperative Nursing Care Scale)

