**Statistical Analysis Plan:**

Descriptive statistics will be used to present characteristics of the study participants. One- and multi-way analysis of variance will be used to compare means of groups. Interaction terms will be used to compare means of the groups defined by combinations of categorical independents. Tukey's adjustment will be used to account for multiple comparison if necessary. Statistical significance of dependencies between categorical variables are tested using Chi-square tests. SAS® statistical software, version 9.4 (SAS Institute Inc., Cary, NC, USA) will be used in statistical analysis.

In the analysis of the patient data, collected with the GPNCS, if a respondent answers to less than 50% of the quality statements, his or her response will be excluded from the analysis. Frequencies and percentages obtained with the Pearson chi-square test are calculated for the background data. Non-parametric tests are used when comparing background factors with quality categories. The reliability of the scale is checked with a Cronbach's alpha coefficient. In the analysis of data sets, the non-parametric tests will include the Kruskall-Wallis test and Mann Whitney U-test with Bonferroni corrections. A *p*-value of 0.05 is considered statistically significant.

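### The Bonferroni correction planned for the GPNCS rank tests is valid but needlessly conservative: Holm's step-down version keeps the same 5% familywise error and can detect more

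*Combined protocol and SAP*

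**What the plan says.** The last paragraph of the Statistical Analysis Plan deals with the GPNCS. It says "Non-parametric tests are used when comparing background factors with quality categories", and then that "the non-parametric tests will include the Kruskall-Wallis test and Mann Whitney U-test with Bonferroni corrections". The significance rule is that a p-"value of 0.05 is considered statistically significant". No step-down procedure is named. The paragraph does not say how many tests are corrected together or which tests form a family, and it plans no simultaneous confidence intervals.

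The only other multiplicity rule is in the first paragraph of the SAP: "Tukey's adjustment will be used to account for multiple comparison if necessary". It follows the analysis of variance and does not reach the rank tests.

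The GPNCS appears under Secondary Outcome Measures as "Quality of perioperative care as experienced by surgical patients", measured once, around discharge.

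**The concern.** Bonferroni corrections ordinarily mean the single-step rule: with k tests, every p-value is compared with 0.05/k. Holm's rule starts at the same 0.05/k for the smallest p-value and relaxes the threshold after each rejection. It needs no further assumption and gives the same familywise guarantee, so for that criterion the single-step rule is never better and sometimes worse.

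At stake is the ability to say in which aspects perioperative care differs. If several comparisons are truly different, the planned rule can leave some of them labelled not significant although the same data and the same 5% familywise error would support them.

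**Working it through.** **1. The plan's own figure.** The only computed design figure is the sample size under Randomization and sample size, from "standard deviation 0.08, and differences of means 0.03 in 15D scores", two-sided alpha 0.05 and power 0.90 (the text prints 0.9 as beta; I read it as power).

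n per group = 2 × (1.960 + 1.282)² × 0.08² / 0.03² = 2 × 10.51 × 7.11 ≈ 149.4, so 150. A t-based calculation gives 151. The stated 152 reproduces to within two patients. It concerns the 15D and is used below only as a group size.

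**2. The two rules.** Order the p-values p(1) ≤ … ≤ p(k).

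- Bonferroni: reject p(j) if p(j) ≤ 0.05/k.
- Holm: reject p(j) if p(i) ≤ 0.05/(k − i + 1) for every i ≤ j.

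Each Holm threshold is at least 0.05/k, so every Bonferroni rejection is also a Holm rejection. The first threshold is identical, so the chance of at least one rejection is identical too.

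Error control: suppose m₀ hypotheses are truly null. When Holm first rejects one of them, at least m₀ hypotheses are still in play, so that p-value is at most 0.05/m₀. The chance that any of m₀ null p-values is that small is at most m₀ × 0.05/m₀ = 0.05, whatever their dependence.

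**3. Examples with k = 3** (Holm thresholds 0.0167, 0.025, 0.05).

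- 0.010, 0.020, 0.040: Bonferroni rejects one, Holm all three.
- 0.010, 0.030, 0.200: both reject one only, because 0.030 > 0.025.
- 0.030, 0.040, 0.045: neither rejects any, because 0.030 > 0.0167.

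**4. Size of the gain.** The documents do not give the number of tests, the GPNCS effect sizes or the correlations, so these are assumptions: 152 per group, two-sided z-tests, standardized difference d = 0.3 for each real effect, correlation 0.5, 200,000 simulated sets. The mean of each real z-statistic is 0.3 × √(152/2) = 2.615. As a check, for k = 7 the Bonferroni critical value is 2.690, giving power P(Z > 2.690 − 2.615) = P(Z > 0.075) = 0.47, as simulated.

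| k | Real effects | Bonferroni, average power | Holm, average power | Gain (points) |
|---|---|---|---|---|
| 1 | 1 | same | same | 0 |
| 3 | 2 | 58.7% | 61.9% | 3.2 |
| 3 | 3 | 58.7% | 66.4% | 7.7 |
| 5 | 2 | 51.6% | 53.2% | 1.6 |
| 5 | 3 | 51.5% | 54.9% | 3.5 |
| 5 | 5 | 51.6% | 61.1% | 9.5 |
| 7 | 4 | 47.0% | 50.4% | 3.4 |
| 7 | 7 | 47.1% | 57.0% | 9.9 |
| 10 | 5 | 42.3% | 45.2% | 2.9 |
| 10 | 10 | 42.5% | 52.4% | 9.9 |

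With one real effect among 3, 5, 7 or 10 tests, the gain was 0.1 point or less.

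**5. What drives the gain.** With k = 7, all real and correlation 0.5, the gain is about 0.5 points at d = 0.1, 3.9 at d = 0.2, 9.9 at d = 0.3 and 0.5 at d = 0.6. At d = 0.3 with all seven real it is 10.0, 10.1, 9.9 and 9.5 points for correlations 0, 0.3, 0.5 and 0.7, so correlation is not the driver there. At d = 0.2 correlation has some influence (1.8 to 4.6 points over the same range). The number of real effects and their size matter most.

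**6. Error.** With all effects null, Holm's familywise error equals Bonferroni's (0.041 at k = 7, correlation 0.5). With four of seven real at d = 0.3 it is 0.032 against 0.020. Both stay below 0.05.

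**The case against.** Four objections have force.

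**The family is unclear.** The SAP describes comparisons of background factors with quality categories. A reader might infer that the intervention-control comparison is among the corrected tests and loses power, but the text does not clearly say so. The correction may instead cover pairwise Mann-Whitney follow-ups of a Kruskal-Wallis test. On that reading a two-group comparison is a single test and nothing changes. This stands as a limit on the consequence. It does not affect the ordering of the two methods, which holds for any family of more than one test.

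**The larger gains are favourable cases.** They need every effect to be real and of moderate size. The 15D planning ratio of 0.03/0.08 = 0.375 is not evidence about the GPNCS. Nor does one questionnaire answered by the same patients show that many categories truly differ. This stands, and the gain must be shown from zero upward.

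**Bonferroni does buy something.** It also bounds the expected number of false positives at 0.05, which Holm does not. With k = 7, all null and correlation 0.7, the expected numbers are about 0.05 and 0.06. With four of seven real at d = 0.6 and correlation 0.5, the familywise error is 0.020 for Bonferroni and 0.044 for Holm. So it would be wrong to say that nothing is given up. But the plan states no such aim, and Holm still meets the 5% familywise level.

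**It is a refinement.** Bonferroni is valid, the outcome is secondary, and either method needs its family defined before it can be applied. That is correct and sets the weight of the point. The change is still a concrete improvement at almost no cost.

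**Conclusion.** The point holds as a minor, nearly free improvement. The SAP names a valid but needlessly conservative correction for the GPNCS rank tests. Holm's procedure is at least as powerful at the same 5% familywise error, with no assumption about dependence.

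How much it would gain here is unknown. With 152 per group, k = 3 to 10 and correlation 0.5, all of them assumptions except the group size, average power rises by nothing to about 10 points, and only the case of several real, moderate effects reaches the upper end.

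A reader might go further and conclude that differences in care quality will be missed, or that the trial's group comparison is compromised. The documents support neither. Differences can be missed, only where one test has already passed 0.05/k and another p-value lies between its two thresholds, and the group comparison is not clearly in the family. The choice is not a type I error problem, and the primary 15D analysis and the sample size are untouched.

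**What to change.** In the last paragraph of the SAP, replace the reference to Bonferroni by: *with Holm step-down correction (familywise alpha 0.05) within each set of tests to which the correction applies*. Report Holm-adjusted p-values, computed as the running maximum of min(1, (k − i + 1) × p(i)) over the ordered p-values.

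The cost is one phrase. The same Kruskal-Wallis and Mann-Whitney p-values are used, with no new data or tests. There are two small downsides: Holm has no equally simple matching simultaneous confidence intervals (none are planned), and Bonferroni's additional bound on the expected number of false positives is given up. The phrase does not itself define the sets of tests; they have to be listed under either method.
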